4.4 Screen Failure

A subject who signs an informed consent form (ICF) and does not have a ReMOTE robotic-assisted PCI or is enrolled in the study but withdraws their consent will be considered a screen failure.

4.5 Patient Selection

Subjects with coronary artery disease with a clinical indication for PCI and deemed appropriate for PCI with the CorPath GRX POP System, and who have signed the ICF for data collection will be enrolled into the GRX with ReMOTE study.

General Inclusion Criteria:

1. Age \geq 18 years;
2. Patients with coronary artery disease with clinical indication for PCI;
3. Patient deemed appropriate for the CorPath GRX POP System; and
4. The subject has been informed of the nature of the study, agrees to its provisions and has provided written informed consent.

Angiographic Inclusion Criteria:

1. Study lesion is a single *de novo* native coronary artery lesion (i.e. a coronary lesion not previously treated).
2. The lesion reference vessel diameter is between 2.50 mm and 4.0 mm by visual estimate.
3. Study lesion length less or equal to 20 mm by visual estimate.
4. The study lesion length can be treated with one stent. The stent should be able to cover the whole length of the lesion with at least 2mm of normal segments on proximal and distal edges of the lesion.
5. Study lesion diameter showing significant stenosis of at least 50% by visual estimate.

NOTE: Patient may have additional lesions requiring treatment using standard PCI (i.e. without utilization of the CorPath device) prior to actual enrollment in the study to perform treatment of study lesion using CorPath device. These non-study lesions must be in different vessel(s) than the study lesion. If non-study lesion(s) are treated on the same day of the index procedure, non-study lesion(s) must be successfully treated prior to the treatment of the study lesion.

General Exclusion Criteria:

1. Failure/inability/unwillingness to provide informed consent; or
2. The investigator determines that the patient or the coronary anatomy is not suitable for robotic-assisted PCI.

Angiographic Exclusion Criteria:

1. Target lesion that cannot be fully covered by a single stent.
2. Subject requires treatment of multiple lesions
3. Any previous stent placement within 5 mm (proximal or distal) of the target lesion.
4. The study lesion requires planned treatment with DCA, laser, rotational atherectomy, or any device except for balloon dilatation prior to stent placement.
5. The study vessel has evidence of intraluminal thrombus or moderate to severe tortuosity (> 90°) proximal to the target lesion.
6. The study lesion has any of the following characteristics:
 - a. Total occlusion
 - b. Within 2mm of a side branch > 2.0 mm vessel diameter
 - c. Not ostial in location
 - d. Is located at 45° bend in the vessel
 - e. Is severely tortuosity
 - f. Is severely calcified
 - g. Severe calcification at the part of the vessel proximal to target lesion
 - h. Target lesion that is in a native vessel distal to an anastomosis with a saphenous vein graft or a left/right internal mammary artery (LIMA/RIMA) bypass and is approached through the by-pass graft.
7. Unprotected left main coronary artery disease (an obstruction greater than 50% diameter stenosis in the left main coronary artery).

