3.4.1 Overall Procedure Time Measure

Defined as the time measured from the insertion of the hemostasis sheath until the removal of the guide catheter

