3.4.3 Fluoroscopy Time

Total fluoroscopy utilized during the PCI procedure, as recorded by an imaging system.

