3.4.5 Contrast Fluid Volume

Total volume used during the PCI procedure.

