4.6 Data to be Collected

4.6.1 Baseline data

The following baseline data *should* be collected for all subjects prior to staged index-procedure (usually routinely done for patients with PCI):

- CK & CK-MB and/or Troponin (within 7 days, select the lab value closest to the CorPath PCI)

Additionally, the following baseline data should be collected for all subjects within 30 days prior to the staged index procedure (usually routinely done for PCI patients):

- Patient Eligibility Criteria
- Medical history
- Clinical assessment & physical examination
- Non-cardiac laboratory tests (Creatinine, Hemoglobin)

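### Same-day manual PCI of another vessel is permitted before the robotic lesion, but no rule separates its time, fluoroscopy, dose, contrast or events from those of the remote procedure

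*Combined protocol and SAP*

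**What the plan says.** The NOTE under the angiographic inclusion criteria (Section 4.5, repeated in the synopsis) allows lesions in other vessels to be treated by standard PCI "prior to actual enrollment in the study to perform treatment of study lesion using CorPath device". It then covers the same-day case: "If non-study lesion(s) are treated on the same day of the index procedure", the requirement is that "non-study lesion(s) must be successfully treated prior to the treatment of the study lesion". Angiographic exclusion 2 in the same section reads "Subject requires treatment of multiple lesions".

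The procedural measures are defined as follows.

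- Overall Procedure Time (3.4.1): "Defined as the time measured from the insertion of the hemostasis sheath until the removal of the guide catheter".
- PCI Procedure Time (3.4.2): guide catheter in to guide catheter out.
- Fluoroscopy (3.4.3): "Total fluoroscopy utilized during the PCI procedure, as recorded by an imaging system". Section 3.4.4 ties DAP and cumulative dose/air kerma to the same interval.
- Contrast (3.4.5): "Total volume used during the PCI procedure". The synopsis instead limits contrast to the CorPath GRX procedure.
- CorPath GRX Procedure Time (synopsis): the guidewire segment of the robotic work only. Section 4.6.2 collects a matching CorPath time.

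For cardiac biomarkers, Section 4.6.1 accepts a value from the previous 7 days, with the instruction to "select the lab value closest to the CorPath PCI". A footnote to Table 1 makes this conditional on a sample having been collected. Section 3.2.2 leaves post-procedure sampling to the investigator.

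**The concern.** Section 8.0 gives the purpose of the study as gathering preliminary performance data on the remote system. If a subject has a manual PCI in another vessel and then the robotic PCI in one session, the recorded time, fluoroscopy, dose and contrast may describe both. Where no reading is taken between the two stages, the parts may not be separable afterwards.

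The primary safety endpoint has a related gap. In-Hospital MACE is counted per subject. Its revascularization component is restricted to the target vessel, but MI and cardiac death are not. An event arising from the manually treated vessel could therefore be charged to the remote system.

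**Working it through.** The plan gives no figure for the size of this effect, so there is none to reproduce. The check compares the measurement windows, follows the MI definition through, and then sizes the effect under a stated assumption.

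**Step 1. Does each measure include manual work done in the same session?**

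| Measure | Window in the plan | Manual work included? |
|---|---|---|
| Overall Procedure Time (3.4.1) | Sheath in to guide catheter out | Yes, if the sheath is shared |
| PCI Procedure Time (3.4.2) | Guide catheter in to out | Unclear; no rule on which catheter counts |
| Fluoroscopy (3.4.3), dose (3.4.4) | The PCI procedure, not delimited | Unclear; no start point |
| Contrast (3.4.5) | The PCI procedure, not delimited | Unclear |
| Contrast (synopsis) | CorPath GRX procedure | No, if followed |
| CorPath GRX Procedure Time (synopsis, 4.6.2) | Robotic guidewire segment | No |
| Device technical success (3.2.1) | Remote robotic PCI | No |
| Residual stenosis (3.2.3) | Robot-treated lesion | No |

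**Step 2. Could the stages be separated afterwards?** Section 4.6.2 records sheath insertion and guide catheter insertion times before CorPath starts. If a new guide catheter is inserted for the study vessel, that gives one usable clock reading. For fluoroscopy, the recommended steps ask only for the final value. No starting value, counter reset or hand-over reading is specified for fluoroscopy, dose or contrast.

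**Step 3. Could an MI from the manual vessel count?** Suppose the latest sample is normal and predates the manual PCI. The normal-baseline branch of 3.2.2 then applies: CK-MB at least 10 times ULN or troponin at least 70 times ULN, or at least 5 and 35 times respectively with new Q-waves or LBBB. A rise of that size from the manual vessel meets the definition. The branches for an elevated or unstable baseline help only if a sample was taken between the stages, and none is required. Section 7.2 provides site-independent adjudication but no rule for assigning an event to a vessel or stage.

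**Step 4. Size.** Inputs: n = 5, the maximum in Section 8.0; k, the number of subjects with same-session manual PCI (assumed); r, the manual part as a fraction of the robotic part (assumed, because the documents give no value). If the robotic part is similar across subjects,

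rise in the study mean = (k / n) × r

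| | r = 25% | r = 50% | r = 100% |
|---|---|---|---|
| k = 1 | 1/5 × 25% = 5% | 10% | 20% |
| k = 2 | 2/5 × 25% = 10% | 20% | 40% |

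For MACE, one misattributed event among 5 subjects moves the observed rate by 1/5 = 20 percentage points, and by more if fewer than 5 are treated.

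**The case against.** The strongest reply is that the scenario is narrow. Subjects are described as staged (4.1, 4.2, 4.6.1). The NOTE places manual PCI before actual enrollment, same day need not mean same session, and the recommended steps in 4.6.2 include no manual non-study stage. If the conflict with exclusion 2 were settled by keeping such patients out, the problem would vanish. All of this limits how often it can arise. It does not close the gap, because the NOTE expressly provides for the same-day case and nothing requires separate sessions.

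A reader might infer that fluoroscopy, dose and contrast are defined as whole-session totals. The documents do not say so. Section 4.6.2 lists all three under data collected during the CorPath procedure, and the synopsis limits contrast to that procedure. The window is undefined, and for contrast it is defined in two ways.

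A reader might also infer that any biomarker rise from the manual PCI becomes a MACE. It does not: the thresholds are high, a baseline not shown to be stable or falling also requires ST changes and clinical signs, sites are told to use the value nearest the CorPath PCI, and endpoint events are independently reviewed. What stands is that a qualifying MI from the manual vessel has no rule keeping it out.

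Finally, the study has no comparator and no pass/fail objective, and contamination would lengthen times and raise dose and contrast, so it would not flatter the system. That limits the consequence to the accuracy of the descriptive results. Those results are what the study is meant to produce.

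**Conclusion.** The point holds as a missing separation rule. When the NOTE is applied within one session, Overall Procedure Time includes the manual work by definition, and PCI Procedure Time, fluoroscopy, dose and the 3.4.5 contrast measure have nothing that keeps it out. An MI that meets the full definition could be counted against the remote system even though the manual vessel caused it.

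It would go too far to say that manual PCI is counted as remote performance throughout. CorPath GRX procedure time, device technical success and residual stenosis all refer to the robotic work alone.

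The 5 to 20% rise for one affected subject in 5 rests wholly on the assumed 25 to 100% manual burden; the number of affected subjects is also assumed. The change is worth making because it is cheap and because readings not taken at the hand-over may be unrecoverable.

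**What to change.** 1. Reconcile the 4.5 NOTE with angiographic exclusion 2, in the synopsis as well. If same-day non-study PCI remains possible, make the changes below.
2. In 4.6.2, for any subject with same-session non-study PCI, record clock time, cumulative fluoroscopy, DAP/air kerma and contrast volume when the study-vessel guide catheter is inserted. State which moment applies if one guide catheter serves both vessels, since there is then no second insertion.
3. For these subjects, report PCI Procedure Time, fluoroscopy, dose and contrast as the increment from that reading.
4. Keep Overall Procedure Time as defined, but list it separately for these subjects. Restarting it at the study vessel for everyone would discard the sheath-to-guide-catheter interval in single-lesion subjects and make it nearly the same as PCI Procedure Time.
5. Use one contrast definition in the synopsis and 3.4.5.
6. Flag same-day non-study PCI on the CRF, and list MACE and procedural data with and without flagged subjects.

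The cost is about one extra CRF line for each affected subject, using equipment already in the room. The flag makes a possible MI misattribution visible but does not resolve it, because it adds no biomarker information between the stages.

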4.6 Data to be Collected

4.6.1 Baseline data

The following baseline data *should* be collected for all subjects prior to staged index-procedure (usually routinely done for patients with PCI):

- CK & CK-MB and/or Troponin (within 7 days, select the lab value closest to the CorPath PCI)

Additionally, the following baseline data should be collected for all subjects within 30 days prior to the staged index procedure (usually routinely done for PCI patients):

- Patient Eligibility Criteria
- Medical history
- Clinical assessment & physical examination
- Non-cardiac laboratory tests (Creatinine, Hemoglobin)

4.6.2 CorPath GRX PCI Procedure

Peri-Procedure Study Medication Regimen

Follow standard institutional and/or stent manufacturer's guidelines for recommended anticoagulation regimen.

Data to be collected prior to initiating CorPath:

- Arterial access site
- Procedure start time (Sheath insertion)
- PCI Start Time (Guide Catheter Insertion)
- Lesion Classification

Data to be collected during the CorPath procedure:

- CorPath time (guidewire activation to guidewire retraction)
- Fluoroscopy time
- Patient radiation exposure (DAP and AK/CD)
- Contrast volume
- Procedure end time (Guide Catheter out)
- Guide catheter manipulation attempts (guide catheter reengagement with CorPath GRX)

CorPath Use Technique

The operator should refer to the CorPath GRX System Operator's Manual for a detailed description of the system and relevant techniques.

To obtain proper data for analysis, the following procedure, with associated data collection milestones, is recommended, but in no case, dictates use of the CorPath POP System in a manner different from that presented in the Operator's Manual:

1. Obtain access using conventional percutaneous catheterization techniques.
2. Once arterial access is obtained, insert a standard guide catheter using conventional techniques. The guide catheter and guidewire of the physician's choosing shall be used.
3. Manually advance and engage the guide catheter in the coronary artery.
4. Perform angiography to assess the target lesion(s).
5. Record target lesion characteristics such as percent diameter stenosis, etc.
6. For Remote operation, the remote Interventional Cardiologist (IC) workstation must be enabled. In general, select which workspace (local or remote) is to be used for the procedure. Only one workspace can have control at a time.

To enable exclusive control:

For the local (Cath lab) side, the local operator should click or tap “Enable All” from the control console. This will lock out access by the remote (IC) operator, and gray out controls on the remote (IC) side. To release control, the local (Cath lab) operator should subsequently click or tap “Disable all”.

For the remote (IC) side, first the IC workstation must be enabled. The remote operator should click or tap “RCL Disabled” (Remote Cath Lab) from the control console. This will lock out access by the local (Cath lab) operator, and gray out controls on the local (Cath lab) side.

Once the IC workstation has been enabled the operator should click or tap “Enable All” from the control console. This will allow control of the IC workstation to proceed.

To release control, the remote (IC) operator should subsequently click or tap “IC Enabled”.

During any procedure (whether controlled remotely or locally), to change devices on the robot arm, or to otherwise lock out joystick controls, the bedside operator should click or tap “Exchange Devices” on the robot console, to disable controls.

The remote or local user can click or tap “Disable All” at any time to lock out the joystick controls.

7. Introduce and advance coronary guidewire to the tip of the guide catheter utilizing CorPath GRX POP System.
8. Introduce and advance the therapeutic coronary device (balloon/stent) using the CorPath GRX POP System. The delivery of interventional dilatation and stenting devices to the target lesion (pre-dilation, stent, post dilatation) will be done using the CorPath GRXPOP System. Active guide management may be used to fine tune the placement of or reengage the guide catheter in the ostium of the coronary artery.
9. Retract balloon/stent system using CorPath GRX POP System.
10. Perform completion angiography to assess the target lesion final diameter stenosis and the condition of associated vasculature.
11. Record final fluoroscopy time.
12. Record time of guide catheter removal from the coronary vessel (**procedure end time**).

4.6.3 Conversion to Manual Procedure Data Collection

The Investigator shall determine if it is necessary to convert to standard manual percutaneous techniques to **complete** the PCI. The Investigator should make this decision based on his/her medical assessment of the situation in accordance with the best interest of the subject. A second physician will be available at the bedside in the event a conversion to manual is necessary. It is recommended that conversion to manual operation be performed at the discretion of the Investigator or if any of the following occur:

- The inability to navigate the guidewire or balloon/stent catheters using the CorPath GRX POP System as intended.
- Any clinical condition that requires rapid medical intervention.

The reason for conversion to manual should be reported by the operator and documented.

4.6.4 Post-CorPath Data Collection

Acute Post-CorPath Procedure Medication Regimen

Follow standard operator and institutional routines for recommended anticoagulation and anti-platelet regimens.

Post-CorPath Procedure Subject Evaluations

- Clinical assessment and physical examination
- Record of all SAEs
- Hemoglobin and Creatinine (Maximum and 48 hours/Discharge levels)
- If clinically indicated as determined by the investigator,
 - 12-lead ECG
 - CK, CK-MB and/or Troponin

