4.7 Follow-Up

The patients will be followed for 48 hours post-procedure or hospital discharge, whichever occurs first. No additional patient contact is required for this study. Data collection must be completed on all subjects before they are discharged from the hospital.

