Access Site Complication: A complication occurring at the access site that requires either local intervention or blood transfusion.

Subacute Thrombosis: An abrupt closure of the target vessel that occurs after the index procedure is completed (and the subject has left the catheterization laboratory) and within 48 hours of the PCI.

Threatened Abrupt Closure: A grade B dissection and >50% diameter stenosis or any dissection of grade C or higher.

Bleeding Requiring Transfusion: Any blood loss requiring transfusion of blood products.

Transfusion without clinical evidence of bleeding will be recorded separately.

Coronary Artery Bypass Graft Surgery (CABG): Classified as emergent, urgent, or elective as follows:

- **Elective:** the subject is clinically stable, and the overall medical condition does not indicate the need for revascularization within forty-eight (48) hours.
- **Urgent:** the subject is clinically unstable and the condition warrants revascularization within two (2) to forty-eight (48) hours.
- **Emergent:** the subject is clinically unstable, and the condition requires immediate revascularization within two (2) hours.

Cardiogenic Shock: Subject presents with systolic blood pressure <80 mm Hg for more than thirty (30) minutes unresponsive to fluids or requiring intravenous pressures or an intra-aortic balloon pump.

CK: Creatine kinase, or creatine phosphokinase.

CK-MB: An iso-enzyme of creatine phosphokinase (CK) with a distinct molecular structure specific as an indicator of myocardial cell injury. It is used to evaluate possible causes of chest pain, to detect and diagnose acute MI and re-infarction, and to monitor the severity of myocardial ischemia.

Vascular Injuries:

- **Dissection:** A tear in a vessel allowing blood to enter the wall of the vessel and split its layers. The result is either an intramural hematoma or aneurysmal dilatation.

Dissection classification per National Heart, Lung and Blood Institute:

- Type A: Radiolucent areas within the coronary lumen during contrast injection, with minimal or no persistence of contrast after dye has cleared.
- Type B: Parallel tracts or double lumen separated by a radiolucent area during contrast injection, with minimal or no persistence after dye has cleared.
- Type C: Contrast outside the coronary lumen, with persistence of contrast in the area after dye has cleared.
- Type D: Spiral luminal filling defects frequently with extensive contrast staining of the vessel.

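### Section 4.6.4 asks for the maximum post-procedure hemoglobin, which is the favourable extreme, and does not ask for the lowest value

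*Combined protocol and SAP*

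**What the plan says.** Section 4.6.1 lists "Non-cardiac laboratory tests (Creatinine, Hemoglobin" among the baseline items, to be obtained "within 30 days prior to the staged index procedure". After the procedure, Section 4.6.4 asks for "Hemoglobin and Creatinine (Maximum and 48 hours/Discharge levels". Table 1 in Section 4.8 repeats the item only as non-cardiac laboratory tests, with one post-procedure mark and no statement of how many samples or which values. Section 4.7 sets the window: "The patients will be followed for 48 hours post-procedure or hospital discharge, whichever occurs first".

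Bleeding can also reach the data as an event. Section 4.6.4 requires "Record of all SAEs". Appendix A defines "Bleeding Requiring Transfusion: Any blood loss requiring transfusion of blood products" and adds that "Transfusion without clinical evidence of bleeding will be recorded separately". It also defines an access site complication by local intervention or transfusion. None of these definitions uses a hemoglobin threshold.

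**The concern.** A single summary rule has been applied to two laboratory values with opposite directions of harm. Kidney injury shows as a rise in creatinine, so its maximum is the value to keep. Blood loss shows as a fall in hemoglobin, so its maximum is the least informative post-procedure value. A site that follows the line literally enters the highest hemoglobin and the last one, and leaves out the lowest unless it happens to be the last.

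Safety is part of the primary objective (Section 3.1), this is a first-in-human study using arterial access, and at most 5 subjects will be treated. Safety review will in practice be patient by patient. Hemoglobin is the only scheduled laboratory measure of blood loss that does not depend on someone first recognising and reporting an event. What is at stake is the recorded size of a fall in hemoglobin, above all a fall that was neither transfused nor reported as an SAE.

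**Working it through.** The plan gives no figure on this point, so there is none to reproduce. The check is a comparison of the sections plus simple algebra.

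**Is the lowest value requested anywhere?** Section 4.6.1 covers baseline only. Section 4.6.4 names the maximum and the 48-hour/discharge level. Table 1 names no particular value. Appendix A uses transfusion, not hemoglobin. No section asks for a minimum.

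**Direction of the error.** Let B be the baseline value, N the lowest post-procedure value, M the highest, and D the 48-hour/discharge value. D is one of the post-procedure values, so N ≤ D ≤ M.

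- True fall: B − N.
- Fall from the recorded maximum: B − M. It is too small by (B − N) − (B − M) = M − N ≥ 0.
- Fall from the recorded discharge value: B − D. It is too small by (B − N) − (B − D) = D − N ≥ 0.

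Both shortfalls are zero or positive, so the recorded fall can equal the true fall or understate it, but cannot overstate it. B cancels, so the 30-day baseline window does not affect this result. If one sample is drawn, M = D = N and nothing is lost. If the discharge value is the lowest, D = N and the discharge value gives the true fall.

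**Illustration.** The documents give no hemoglobin values, so these are assumptions: B = 14.0, M = 13.5, N = 8.5 g/dL, with a rise from the lowest value to discharge of 0, 1.0 or 3.0 g/dL.

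| Rise before discharge | D | True fall (B − N) | Fall from maximum (B − M) | Fall from discharge (B − D) | Shortfall of the discharge-based fall (D − N) |
|---|---|---|---|---|---|
| 0 | 8.5 | 14.0 − 8.5 = 5.5 | 14.0 − 13.5 = 0.5 | 14.0 − 8.5 = 5.5 | 0 |
| 1.0 | 9.5 | 5.5 | 0.5 | 14.0 − 9.5 = 4.5 | 1.0 |
| 3.0 | 11.5 | 5.5 | 0.5 | 14.0 − 11.5 = 2.5 | 3.0 |

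The maximum is uninformative in every row. The discharge value is exact in the first row and loses ground as recovery or correction before discharge increases.

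**What the event routes cover.**

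- Transfused bleed: meets the Appendix A definition whatever hemoglobin is entered.
- Access-site bleed treated locally: meets the access site complication definition.
- Fall judged serious: recorded as an SAE (Sections 3.3.1 and 4.6.4).
- Fall neither transfused nor treated locally at the access site, and not judged serious: meets none of these. Table 1 schedules SAEs only, and the procedural-event documentation in Section 7.1 depends on someone recognising an event. If hemoglobin also recovers before discharge, the laboratory record understates the fall as well.

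**The case against.** The strongest case against is that little is lost in practice. The same line also requires the 48-hour/discharge value, which records a persisting fall. Table 1 shows one post-procedure mark for laboratory tests and the window is at most 48 hours, so many subjects may have a single sample, and then the rule does no harm. The illustration needs several samples and a rise before discharge. No primary or secondary endpoint uses hemoglobin, Section 8.0 specifies no analysis of hemoglobin change, and monitors have access to hospital charts under Section 6.4. All of this stands, and it limits the size of the point. It does not rescue the rule. Asking for a maximum as well as a discharge value already allows for more than one sample, and when there is more than one, the extreme requested is the wrong one for hemoglobin.

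A reader might infer that the lowest hemoglobin can never be captured, or that a transfused bleed would be hidden. The documents support neither. The lowest value is recorded whenever it is the discharge value or the only sample, and Appendix A identifies a transfused bleed by the transfusion itself. A reader might also infer that the case report form repeats the error. The forms in Appendix C are not shown, so that cannot be said either way.

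**Conclusion.** The point holds as a minor one. As written, Section 4.6.4 requests the favourable extreme of hemoglobin and does not request the adverse one. Where several samples are drawn and hemoglobin rises before discharge, the recorded fall is too small by the amount of that rise if taken from the discharge value, and by M − N if taken from the maximum. How often this will happen cannot be judged from the documents, because the number of post-procedure samples is not stated. The loss is confined to the measured size of the fall, and matters mainly for falls that are not transfused and not reported as SAEs. No named endpoint changes. The conclusion rests on reading the word maximum as applying to both analytes, which is how the line is written.

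**What to change.** Split the line in Section 4.6.4, for example: *Hemoglobin: minimum and 48-hour/discharge values, each marked as taken before or after any transfusion. Creatinine: maximum and 48-hour/discharge values.* If the case report form follows the current wording, change its hemoglobin field to match. If it already asks for the lowest value, align the protocol with it. Where hemoglobin change is described in the report, describe it as baseline to minimum, with the discharge value alongside.

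The cost is a split line and one or two extra data fields. No additional blood draw is needed, and no endpoint or patient management is affected.
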